### 13.2 AE Causality Definitions

TERM	DEFINITION	CLARIFICATION
Unrelated	This category applies to those AEs which, after careful consideration, are clearly due to extraneous causes (disease, environment, etc.)	
Possibly	This category applies to those AEs for which, after careful medical consideration at the time they are evaluated, a connection with the test drug administration appears unlikely but cannot be ruled out with certainty.	An AE may be considered possibly related if or when (at least two of the following): 
 
• It follows a reasonable temporal sequence from administration of the drug.
 
• A causal relationship to the experimental treatment cannot be reasonably excluded and an alternative explanation (e.g., concomitant medication or concomitant disease) cannot be excluded or reasonably suggested as causing the AE.
 
• It follows a known pattern of response to the test drug.
 

Probably	This category applies to those AEs which, after careful medical consideration at the time	An AE may be considered probably related if or when (at least three of the following):

TERM	DEFINITION	CLARIFICATION
	they are evaluated, are felt with a high degree of certainty to be related to the test drug.	
 
• It follows a reasonable temporal sequence from administration of the drug.
 
• It could not be reasonably explained by the known characteristics of the subject's clinical state, environmental or toxic factors or other modes of therapy administered to the subject.
 
• It disappears or decreases on cessation or reduction in dose. There are important exceptions when an adverse event does not disappear upon discontinuation of the drug, yet drug-relatedness clearly exists.
 
• It follows a known pattern of response to the test drug.
 

In case of an AE, the Investigator will initiate appropriate treatment according to his medical judgment and will decide whether to withdraw the subject from the study. Subjects should be followed clinically until all parameters (including laboratory tests) have either returned to normal, or are otherwise explained.

An abnormal result of diagnostic procedures including abnormal laboratory findings will be considered an AE if it:

- results in subject's withdrawal by the Investigator
- is associated with a serious adverse event
- is associated with clinical signs or symptoms
- is considered by the physician to be of clinical significance

All adverse events will be recorded in the source documents for all study subjects from the signing of the ICF until the subject has completed the study (i.e., following completion of Visit 7 (week 14) or screen fails or prematurely discontinues from the study, whichever occurs first. For randomized subjects all adverse events will be recorded in the eCRF. For screen failure subjects, adverse events will be captured only in the source documents and not in the eCRF.

### 13.3 Reporting Orthostatic Hypotension as AE

Only the following instances of orthostatic hypotension need to be recorded as an adverse event:

- Any drop in systolic or diastolic blood pressure that the PI deems is clinically significant. The decision could be based on observations during the visit or if a subject complains of symptoms related to orthostatic hypotension, however, this is left ultimately to the judgment of the PI.
- A drop of over 30 mm Hg in systolic or 20 mm Hg in diastolic blood pressure should automatically be considered as clinically significant, even if asymptomatic, and thus should be captured as an adverse event.

### **13.4 Serious Adverse Event (SAE)**

An SAE is defined as an AE that results in any of the following outcomes:

- death
- life-threatening
- requires inpatient hospitalization or prolongs hospitalization
- persistent or significant disability/incapacity
- a congenital abnormality or birth defect
- an important medical event which requires medical intervention to prevent the above outcomes.

Important medical events are those which may not be immediately life-threatening, but may jeopardize the subject and may require intervention to prevent one of the other serious outcomes listed above. Examples of such events are intensive treatment in an emergency room or at home for allergic bronchospasm; blood dyscrasias or convulsions that do not result in hospitalization; resulting in an adverse event will normally be considered serious by this criterion.

### **13.5 SAE Reporting**

Any AE meeting the definition of serious, occurring after signing of informed consent or during 30 days after the last dose administration and, from then on, only if the study treatment is assessed as “suspected” with regard to causality, must be recorded on the SAE Report Form provided by PRA Health Science. The SAE must be reported within 24 hours from the Investigator’s knowledge of its occurrence to:

Sites in Europe:

PRA Drug Safety Centre Email (EAPA): [[contact]](mailto:[contact])

PRA Drug Safety Centre Fax (EAPA): [name]

PRA Safety Helpline EAPA: [contact]

Sites in USA and Canada:

PRA Drug Safety Centre Email (NA): [[contact]](mailto:[contact])

PRA Drug Safety Centre Fax (NA): [name]

PRA Safety Helpline NA: [name]

The Investigator must be prepared to supply the sponsor with the following information:

- a) Investigator name and center number
- b) Subject ID number
- c) Medication kit number
- d) Subject initials
- e) Subject demographics
- f) Clinical Event
- g) description

- h) date of onset
- i) severity
- j) treatment (including hospitalization)
- k) relationship to study drug (causality)
- l) action taken regarding study drug
- m) if the SAE was Fatal or Life-threatening  
cause of death (whether or not the death was related to study drug)  
autopsy findings (if available)
- n) Medical History case report form (copy)
- o) Concomitant Medication case report form (copy)
- p) Any relevant laboratory reports

Follow-up information or new information about any SAE should be forwarded by the site to PRA Health Science Safety within 24 hours of the information becoming available. This information should be sent to the sponsor's appointed safety monitor.

The clinical site will be responsible for notifying their IRB and the subject's General Practitioner of all SAEs that occur at their site.

The sponsor/CRO will submit a summary of the clinical course of the SAEs to the authorities, according to regulations.

Subjects who have had an SAE must be followed clinically until all parameters (including laboratory) have either returned to normal, stabilized or are otherwise explained.

**Overdose:**

Taking more than 1 capsule per day and/or more than 4.5 mg of pramipexole ER or matching placebo is considered an overdose. Cases of overdose, whether accidental or intentional, that result in serious adverse reactions are to be reported as an SAE within one business day after the Investigator becoming aware of the overdose. The overdose should be reported on the standard SAE report form and sent to PRA Safety using the information below.

Sites in Europe:

PRA Drug Safety Centre Email (EAPA): [[contact]](mailto:[contact])

PRA Drug Safety Centre Fax (EAPA): [name]

PRA Safety Helpline EAPA: [contact]

Sites in USA and Canada:

PRA Drug Safety Centre Email (NA): [[contact]](mailto:[contact])

PRA Drug Safety Centre Fax (NA): [name]

PRA Safety Helpline NA: [name]

All cases of overdoses, even if not associated with adverse reactions, shall be recorded within EDC, including symptoms, corrective treatment and outcome of overdose.

### **13.6 Pregnancy**

Should a pregnancy occur, it must be reported and recorded on a pregnancy report form. However, pregnancy is not regarded as an AE for the purposes of this protocol, unless there is a suspicion that the study drug may have interfered with the effectiveness of a contraceptive medication.

The outcome of all pregnancies (i.e., spontaneous miscarriage, elective termination, normal birth or congenital abnormality) must be followed up and documented even if the subject was discontinued from the study.

All reports of congenital abnormalities/birth defects are to be considered SAEs. Spontaneous miscarriages should also be reported and handled as SAEs. Elective abortions without complications will not be regarded as AEs.

### **13.7 Suspected Unexpected Serious Adverse Reaction (SUSAR)**

Adverse reactions are all untoward and unintended responses to the investigational product related to any dose administered. Unexpected adverse reaction is those of which the nature, or severity, is not consistent with the applicable product information.

All SUSARs should be reported to the authorities.

Investigators will also be notified of all unexpected, serious, drug-related events (i.e., 7- or 15-day expedited safety reports) that occur during the clinical trial; those events will be reported to the site in a blinded fashion. Each site is responsible for notifying its IRB of these expedited safety reports, in accordance with applicable site practices.

## **14 DATA MANAGEMENT AND QUALITY ASSURANCE**

### **14.1 Handling of Data**

An Electronic Data Capture (EDC) system to collect subject electronic Case Report Form (eCRF) information will be used. All the information collected during the study will be recorded in the eCRF identified by subject initials and subject ID number, for each subject enrolled, including those removed for any reason after administered the first dose. It is the responsibility of the Investigator and Co-Investigator to ensure that the eCRFs are properly and completely filled in.

Central data management will be performed by PRA. Internet-based remote data capture will be used for entering, managing, and validating data from centers. The following regulation will be followed:

- FDA 21CFR part 11 rule
- ICH, Good Clinical Practice, Consolidated guideline
- FDA Guidance for Industry “Computerized system used in clinical trials.
- EU Directives

## **14.2 Coding of Adverse Events, Drugs and Diseases**

All AEs will be coded using the Medical Dictionary for Regulatory Activities Terminology (MedDRA) latest version. Concomitant medications will be coded according to the WHO drug dictionary.

## **14.3 Data Quality Assurance**

All aspects of the study will be carefully monitored with respect to Good Clinical Practices (GCP) and SOPs for compliance with applicable government regulations. The study monitor will be an authorized individual designated by the Sponsor. The study monitor will have access to all records necessary to ensure integrity of the data and will periodically review the progress of the study with the PI. Study monitoring will be conducted according to a monitoring plan.

# **15 STATISTICAL METHODOLOGY**

This study is a phase 3, twelve-week, multi-center, multinational, randomized, double-blind, double-dummy, parallel group study. Up to 525 eligible subjects with early untreated Parkinson's disease (PD) who are not early terminated from the study during screening or baseline visits and are randomized to treatment with P2B001 0.6/0.75 (150 subjects), or pramipexole 0.6 mg once daily (150 subjects), or rasagiline 0.75 mg once daily (150 subjects), or pramipexole ER titrated to therapeutic optimal dose (75 subjects) using a randomization scheme of 2:2:2:1, respectively.

Randomization will take place following the completion of all screening procedures including subject approval by both site PI and the central EMC.

This study is powered to demonstrate the superiority of (i) P2B001 0.6/0.75mg as compared to its individual components in the change from baseline to Week 12/Treatment Termination in Total UPDRS score and, (ii) to demonstrate the superiority of P2B001 0.6/0.75mg over pramipexole ER in the change from baseline to Week 12/Treatment Termination in the ESS.

Treatment with pramipexole ER will serve as a calibration arm to better characterize P2B001 against currently used therapy. Therefore, with the exception of change from baseline to Week 12/Treatment Termination in the ESS, only descriptive statistics and no formal significance testing will be made between the pramipexole ER arm and the other three study arms.

Week 12/Treatment Termination is defined for all statistical analyses involving significance testing as the last visit in which a subject was treated with the study drug.

## **15.1 Sample Size Rationale**

The study was powered to allow achieving two goals:

- To demonstrate the superiority of P2B001 0.6/0.75mg compared to its individual components in the primary endpoint, the change from baseline to Week 12/Treatment Termination in total UPDRS score:

- The power to meet the primary endpoint was estimated based on simulation runs assuming equal arms size of P2B001 0.6/0.75mg and its individual components as well as repeated UPDRS measurements at baseline, week 4, week 8 and week 12.
- The expected STD of the change from baseline was assumed to be 6.0 UPDRS points.
- The expected treatment effect of P2B001 0.6/0.75mg is 3 UPDRS points over rasagiline 0.75mg and 2.25 UPDRS points over 0.6mg pramipexole.
- Sequential correlations between changes from baseline will be 0.7 and 0.49 between these obtained at week 4 and at week 12.
- Missing observations rate of 10% occurring at random.
- The statistical model used in the simulation study was the Mixed Model for Repeated Measures (MMRM) (SAS® MIXED procedure with REPEATED sub-command) testing two contrasts: P2B001 0.6/0.75mg vs. rasagiline 0.75mg and P2B001 0.6/0.75mg vs. pramipexole 0.6mg at Week 12/Treatment Termination.
- In order to consider the study as successful both tested contrasts have to be statistically significant at 5% two-tailed each.

The simulation indicates that a total of 150 subjects per group treated with P2B001 0.6/0.75mg, rasagiline 0.75mg arm or pramipexole 0.6mg will provide 87.6% power to detect a statistically significant effect size favoring P2B001 0.6/0.75mg by 3 UPDRS points over rasagiline 0.75mg and 2.25 UPDRS points over pramipexole 0.6mg.

- To demonstrate the superiority of P2B001 0.6/0.75mg over pramipexole ER in the first secondary endpoint, namely, the change from baseline to Week 12/Treatment Termination in the ESS:
  - The power to meet this secondary endpoint was estimated using the two-sample t-test for mean difference at a two-sided alpha of 5% (SAS® POWER procedure).
  - The expected STD of the change from baseline was assumed to be 3.0 ESS points.
  - The expected treatment effect of P2B001 0.6/0.75mg over pramipexole ER is 1.5 ESS points.
  - According to the gate keeping method for multiple endpoints while testing for the secondary endpoints, this secondary endpoint will be considered as met only in the case that both primary endpoint contrasts as well as the P2B001 0.6/0.75mg over Pramipexole ER comparison in the change from baseline to Week 12/Treatment Termination in the ESS will be met at two-tailed alpha level of 5% each.

This analysis indicates that a total of 150 subjects per group treated with P2B001 0.6/0.75mg and 75 subjects treated with pramipexole ER arm, considering the above assumptions, will provide a power of 94.1% to detect a statistically significant effect size at the magnitude of 1.5 ESS units or more at a two-sided alpha level of 5%.

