### **15.5 Overall Significance Level and Multiplicity Adjustment:**

The overall significance level for this study will be 5% using two-tailed tests. No interim analyses or futility analyses are planned for this study.

The overall, experiment-wise type-I error rate of 5% will be preserved according to the below plan:

1. The principal analysis of the primary endpoint is designed to demonstrate the efficacy of P2B001 0.6/0.75mg as compared to its individual components in the changes from baseline to Week 12/Treatment Termination. Accordingly, analysis will employ two contrasts: P2B001 0.6/0.75mg vs. pramipexole 0.6mg once daily and, P2B001 0.6/0.75mg vs. rasagiline 0.75mg once daily. The type-I error of 5% for multiple contrasts testing for the primary endpoint will be preserved by determining that the primary endpoint is met only if both comparisons will favor P2B001 0.6/0.75mg at a two-tailed alpha level of 5% each.
2. Multiplicity adjustment for multiple endpoints testing for the secondary endpoints will utilize the gate keeping hierarchical method according to the following order and plan:
  - For the 1st secondary endpoint, namely, the P2B001 0.6/0.75mg vs. Pramipexole ER contrast in the change from baseline to Week 12/Treatment Termination in the ESS, will be considered as met only if both primary endpoint contrasts as above defined and the P2B0011 0.6/0.75mg vs. pramipexole ER contrast in the change from baseline to Week 12/Treatment Termination in the ESS will all be met (total of 3 contrasts) at a two-tailed alpha level of 5% each.
  - The 2nd secondary endpoint, namely, the change from baseline to Week 12/Treatment Termination visit in the Total PDQ39 will be considered as met if all of the 3 previous tested contrasts (primary endpoint and 1st secondary endpoint) as well the two contrasts: P2B001 0.6/0.75mg vs. pramipexole 0.6mg once daily and, P2B001 0.6/0.75mg vs. rasagiline 0.75mg once daily in the 2nd secondary endpoint will all be met (total of 5 contrasts) at a two-tailed alpha level of 5% each.

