#### **15.6.10 Key Secondary Efficacy Endpoints and Analyses**

All efficacy endpoints will be tested for the ITT analysis. Secondary endpoints will be tested once both primary endpoint contrasts (P2B001 0.6/0.75mg as compared to its individual components) will favor P2B001 0.6/0.75mg at a two-tailed alpha level of 5% each.

Multiplicity adjustment for multiple endpoints testing for the secondary endpoints will utilize the gate keeping hierarchical method according to the following order and plan:

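### The 94.1% given as the power to meet the first secondary endpoint (ESS against pramipexole ER) is the power of the ESS contrast alone; as the endpoint is defined, the power is about 82-83%

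*Protocol*

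**What the plan says.** Section 15 of the protocol names two goals that the study is powered for. The first is superiority over the individual components on total UPDRS. The second is "ii) to demonstrate the superiority of P2B001 0.6/0.75mg over pramipexole ER in the change from baseline to Week 12/Treatment Termination in the ESS".

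Section 15.1 then takes each goal in turn. For the primary endpoint it lists the assumptions and the success rule (both contrasts significant at two-tailed 5%) and concludes that 150 subjects per arm "will provide 87.6% power to detect a statistically significant effect size favoring P2B001 0.6/0.75mg by 3 UPDRS points over rasagiline 0.75mg" and by 2.25 points over pramipexole 0.6 mg.

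The ESS block follows the same pattern. It opens: "The power to meet this secondary endpoint was estimated using the two-sample t-test for mean difference at a two-sided alpha of 5" per cent. On spread it says: "The expected STD of the change from baseline was assumed to be 3.0 ESS points". The expected difference is 1.5 points. The next item in the list is the success rule: "this secondary endpoint will be considered as met only in the case that both primary endpoint contrasts as well as" the ESS comparison are significant at two-tailed 5% each. The conclusion, for 150 and 75 subjects, is "considering the above assumptions, will provide a power of 94.1% to detect a statistically significant effect size at the magnitude of 1.5 ESS units". The synopsis carries the same text.

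The rule is repeated in section 15.5, where the endpoint "will be considered as met only if both primary endpoint contrasts as above defined and the" ESS contrast all succeed (three contrasts in total). Section 15.6.10 also has it: "Secondary endpoints will be tested once both primary endpoint contrasts" favour P2B001. No joint power for the three contrasts appears in the protocol or in the SAP addendum.

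**The concern.** A power to meet an endpoint should be the probability that the endpoint is met as the plan defines it. Here that requires three significant contrasts. The protocol itself gives only 87.6% for the first two, so 94.1% cannot be the probability of all three.

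The ESS comparison is one of the two stated powering goals and the only formal significance test against pramipexole ER within the multiplicity plan. Under section 15.5, every later secondary endpoint also depends on it. A sponsor or agency reading 94.1% would put the risk of missing this goal at 100 - 94.1 = 5.9%. On the protocol's own figures that risk is about three times as large.

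**Working it through.** **Inputs, all from section 15.1**
- ESS: 150 against 75 subjects, difference 1.5, SD 3.0, two-sample t-test, two-sided 5%, stated power 94.1%.
- Primary: 150 per arm, differences 3 and 2.25, SD 6.0, correlations 0.7 between successive visits and 0.49 between first and last, 10% of observations missing at random, both contrasts required, stated power 87.6%.

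**Step 1. Reproduce 94.1%.**
- Noncentrality = 1.5 / (3.0 x sqrt(1/150 + 1/75)) = 1.5 / (3.0 x sqrt(0.02)) = 3.536, with 150 + 75 - 2 = 223 degrees of freedom.
- The noncentral t distribution gives power 0.9407, and the normal approximation 0.9424. A one-sided 5% test would give 0.970.
- So 94.1% is the two-sided power of the single ESS contrast, with all 225 subjects evaluable and no prior condition.

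**Step 2. Confirm that 87.6% is a joint power.**
- The stated correlations and 10% random missingness give an effective week-12 sample size of 141.6 per arm.
- The noncentralities are 3 / (6 x sqrt(2/141.6)) = 4.21 and 2.25 / (6 x sqrt(2/141.6)) = 3.15. The contrasts have correlation 0.5 because they share the P2B001 arm.
- The bivariate normal probability that both are significant is 0.878, against the stated 0.876. The primary figure therefore does include its own success rule.

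**Step 3. Combine the two stated figures without assuming anything about dependence.**
- Upper bound: min(0.876, 0.941) = 0.876.
- Lower bound: 0.876 + 0.941 - 1 = 0.817.
- Independence: 0.876 x 0.941 = 0.824.

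**Step 4. Allow for the shared P2B001 arm.**
- Let rho be the within-subject correlation between the UPDRS and ESS changes. The documents do not give it, so it is shown as a range.
- In units of the outcome variances, the covariance of a UPDRS contrast with the ESS contrast is rho/150. The variances are 2/150 and 1/150 + 1/75 = 3/150. The correlation between the contrasts is therefore rho / sqrt(2 x 3) = rho / sqrt(6) = 0.408 x rho.
- The two primary contrasts are scaled to a joint power of exactly 0.876 (noncentralities 3.144 and 4.192), and the ESS contrast is set to 0.941.

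| rho | Probability that all three contrasts are significant |
|---|---|
| -1 | 0.818 |
| -0.5 | 0.820 |
| -0.3 | 0.822 |
| 0 | 0.824 |
| 0.3 | 0.828 |
| 0.5 | 0.830 |
| 1 | 0.839 |

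Simulation with one million draws agrees: 0.821, 0.824, 0.828 and 0.831 at rho of -0.3, 0, 0.3 and 0.5.

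**Step 5. Size of the discrepancy.**
- Overstatement: 94.1 - 83.0 = 11.1 to 94.1 - 82.0 = 12.1 points. Even at the upper bound it is 94.1 - 87.6 = 6.5 points.
- Chance of not meeting the endpoint: about 17% to 18%, and between 100 - 87.6 = 12.4% and 100 - 81.7 = 18.3% under any dependence.

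**The case against.** The best defence is that nothing is hidden. The sentence carrying 94.1% speaks only of detecting a significant ESS effect, which is accurate for that contrast. The method is named as a two-sample t-test, which could not contain two UPDRS contrasts. The hierarchical rule and the 87.6% stand in the same section, so a reader can combine them. The rule can also be read as a decision rule rather than one of the assumptions.

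There is also a reading under which 94.1% is about right, namely as the power of the ESS test once the primary has succeeded. On the figures above, that conditional power is 0.820/0.876 = 93.6% to 0.830/0.876 = 94.7%. Quoting power step by step in a hierarchy is legitimate if it is labelled so.

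This establishes that the fault is a label and not an arithmetic slip. It does not rescue the label. The opening line promises the power to meet the endpoint, and the same list then defines what meeting it requires. The parallel primary block reports a power that does respect its own success rule, so a consistent reader will take 94.1% the same way.

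One further point stands as a caveat: 87.6% allows for 10% missing observations, whereas 94.1% assumes complete data. If the same missingness and correlations are assumed for ESS under the planned repeated-measures model (effective 141.6 and 70.8 subjects), the ESS contrast alone has power 0.928 and the joint figure is 0.808 to 0.820. That calculation takes no credit for the baseline ESS covariate; a baseline-change correlation of about 0.24 would offset the loss. This is a sensitivity check only, and the conclusion does not rest on it.

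**Conclusion.** The concern holds. The 94.1% is the correct power of the ESS contrast alone and is mislabelled as the power to meet the endpoint. As the protocol defines the endpoint, the power cannot exceed 87.6% and cannot fall below 81.7%; both limits follow from the protocol's two stated figures alone. The realistic value is about 82-83%, assuming normally distributed contrasts that share the P2B001 arm and a UPDRS-ESS correlation of -0.5 to 0.5. Over the whole range of that correlation the figure stays between 81.8% and 83.9%, so the conclusion does not depend on it.

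The consequence is confined to how likely one of the two stated goals is to be met. Sample size, order of testing, type I error control and analysis are not affected. SAP version 2.0 is not among the documents (only its addendum is), so whether it restates this power could not be checked.

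**What to change.** Make two edits, each in the synopsis sample-size text and in section 15.1:

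1. Reword the opening of the ESS power item to: *The power of the ESS contrast alone, before gatekeeping and with complete data, was estimated ...*
2. After the sentence with 94.1%, add: *Under the gatekeeping rule, the power to meet the first secondary endpoint (both primary contrasts and the ESS contrast) is about 82%, and at most 87.6%.* It would help to note there that this combines the stated 87.6%, which allows for 10% missing observations, with the complete-data 94.1%.

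The cost is one reworded and one added sentence in two places, and a less favourable headline figure. Nothing in the conduct, sample size, test order or analysis changes. If SAP version 2.0 restates the figure, it needs the same wording.
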